were below 30 both at baseline and 6 months for 8/14 cases, and these 8 cases correlated well with change in Ki-67. Figure 7 plots the relative expression for pS2 (6 month value/baseline) vs. change in Ki-67 expression (6 months – baseline). It is encouraging that pS2 (an estrogen responsive gene) was generally reduced (values less than 1) when Ki-67 was decreased (negative values), supporting the hypothesis that we are lowering estrogen at the tissue level despite continuing systemic administration of hormone replacement therapy.

Figure 7: Comparison of Changes in Ki-67 vs. pS2 Expression.

[figure not shown]
Nuclear Morphometry

A developmental study in collaboration with the University of Arizona was conducted to examine quantitative nuclear morphometry (karyometry) as a means of describing the proportion of abnormal cells before and after prevention intervention. Papanicolaou-stained ThinPrep slides of RPFNA samples from 11 subjects were digitally recorded at high resolution with 200 cells measured in each slide, at baseline and at 6 months. The nuclear chromatin pattern was assessed for its characteristics by multivariate analytic techniques; a determination of nuclear abnormalities was carried out and procedures were applied that allowed the identification of a subpopulation on cells which showed expression of abnormality. This provided an estimate of 6.6 % of abnormal cells at base line, and of 1.6 % at 6 months, indicating a decrease in the frequency of abnormal cells following treatment with letrozole. The slides from the remaining 31 subjects are being analyzed for a validation of this preliminary result. These results will provide the algorithm for blinded (sequence of slides and study agent assignment) analysis of specimens from the proposed trial.

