10.4 RNA Extraction and qRT-PCR Assessments

RNA extraction will be performed after microdissection of the third slide using an Acturus Autopix and Macro LCM caps (Arcturus, Mountain View, California). RNA from microdissected epithelial cells and residual whole slide scraping is obtained using a commercial protocol (Paradise Reagent Solution, Arcturus) optimized for formalin-fixed specimens [Petroff 2006B]. Material is heated in an overnight incubation with proteinase K to lyse cells and dissociate nucleic acids prior to harvesting. RNA is isolated using column based chromatography and treated with DNase to eliminate any residual DNA. Purified RNA is amplified with a single round of T7 based linear amplification (Paradise Reagent System, Arcturus) and converted to cDNA and stored at -80°C until all specimens from a subject can be run in a single batch. Quality of RNA is checked by PCR (QC Metric, Arcturus). The quantity of RNA is expressed relative to the level of that for a housekeeping gene. The housekeeping gene differed by type of marker to be detected. Markers expected to be in relatively high abundance (e.g., ER, Cyclin D1) were tested against actin which is highly expressed. Markers expected to be expressed in relatively low levels (e.g., proliferation markers, pS2, aromatase) were tested against TATA box binding protein (TBP), a housekeeping gene that is expressed at low levels. PCR reactions were run on an Applied Biosystems Prism 7000 Sequence Detection System. PCR values obtained with crossing threshold (CT) values if fewer than 30 cycles were considered valid for analysis [Giulietti 2001; Feldman 2002; Gjerdrum 2004; Goldworthy 1999; Liss 2002; Al-Taher 2000; Liviak 2001; DeCremoux 2003].

The primary purpose of qRT-PCR assessments on extracted RNA is to a) confirm presence of the targets for letrozole (aromatase) and estradiol (ER); b) provide indirect evidence of reduction in breast tissue estradiol through assessment of the estrogen response genes pS2 (trefoil factor-1) and GREB-1 [Rae 2005].

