10.5.3 Cardiovascular and Bone Fracture Risk Biomarkers

The combination of high sensitivity C-reactive protein and total cholesterol:HDL ratios provide excellent risk biomarkers for cardiovascular disease [Ridker 2005]. Lipid panel with total cholesterol:HDL ratio is performed on serum by an enzymatic assay after a 12 hour fast. High sensitivity C-reactive protein, an indicator of inflammation, will be performed by an immunochemiluminometric assay.

N-telopeptide crosslinks correlate with the rate of bone reabsorption and bone mineral density in osteoporotic women and can be used to monitor the efficacy of anti-reabsorptive therapy with estrogen and calcium [Greenspan 2000]. The test is performed on serum by EIA. Mean values for women are 12.6 nM BCE/L (6.2 – 19.0 nM BCE/L).

Osteocalcin is a measure of bone/reabsorption. It together with the N-telopeptide is helpful in determining reduction in bone turnover in response to anti-reabsorptive agents or predicting early bone mineral loss after hormone therapy is stopped. The test is performed on serum by an immunochemiluminometric (ICMA) assay [Slovik 1984]. It is best performed fasting as it cannot be performed on a lipemic specimen.

The above assays will be performed at LabCorp Inc. Research Division or a similar CLIA-approved laboratory.

Estrogen supplementation increases high density lipoproteins and thus it is possible that administration of letrozole will result in a higher total cholesterol:HDL ratio. We do not expect any difference in change in C-reactive protein, osteocalcin, or N-telopeptide between letrozole and placebo groups.

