12.1 Sample Size and Power

The primary outcome of interest is efficacy of letrozole relative to the placebo, thus the pre- to post-treatment change in a proliferation index (percent of cells expressing Ki-67) is the basis of the power analyses. From our pilot study, the average percentage of cells expressing Ki-67 at baseline was 6.4%, and the average change in percent of cells expressing Ki-67 was a 3.7% reduction, for subjects meeting the same eligibility requirements as will be used in this proposed trial.

A 1:1 randomization of 96 evaluable subjects will provide 90% power to detect an effect size of 0.67 standard deviations with a Type I error rate of 5% using a two-sample, two-sided t-test. In other words, if one assumes a common standard deviation of change of 5.5% (as observed in the pilot study for the 33 subjects matching eligibility criteria for the proposed trial) for both placebo and letrozole groups and if mean change for placebo is zero, then there will be 90% power to detect an average change of 3.7% in Ki-67 in the letrozole group with a Type 1 error rate of 5%. Note that the 3.7% reduction is what was seen in the pilot study. Using a conservative drop-out rate of 10% (it was 2% in the pilot study), enrollment of 108 subjects should provide the required 96 evaluable subjects for the primary endpoint.

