12.2 Statistical Analysis

All analyses will be intent-to-treat. All subjects randomized will be evaluable for safety and all subjects that have both a pre and post specimen are evaluable for efficacy. Primary analysis of efficacy will be performed on all evaluable subjects and secondary analysis will be done on those subjects who received at least 3 months of study medication. From our experience we have very little missing data, however, if the missing data rate is above 5%, we will use multiple imputation to impute these values to perform the primary and secondary analyses.

The primary outcome will be change in Ki-67 (percent of cells expressing Ki-67) from baseline to 6 months. The two-sample t-test will be used to compare the change in Ki-67 between the letrozole and placebo groups. Any difference in baseline values of Ki-67 between the two groups would

be due to chance, however, if there is a significant difference, then analysis of covariance adjusting for baseline values will be performed. Due to potential skewness in these variables we will assess whether or not the Central Limit Theorem may be assumed. Given the sample size the existence of an extremely high degree of skewness would require the use of the Wilcoxon Signed Rank test.

For the secondary endpoints, similar methods as above will be used to compare the treatment and control groups at two time points for all markers, i.e., serum hormones, mammographic breast density, and clinical laboratory tests. We will also correlate change in the primary biomarker Ki-67 with change in other markers (e.g., bioavailable estradiol, pS2, GREB-1) using Pearson's correlation coefficient. Again, if there exists a high degree of skewness in these variables, Spearman's correlation will be utilized.

Multiple regression analysis will also be used to investigate whether changes in Ki-67 are due to variables other than treatment effect (e.g., age, cytomorphology, Gail risk; as well as the predictive effect of other biomarkers on modulation of Ki-67). Best subsets and stepwise approaches will be employed while controlling for treatment group.

For comparison of moderate or worse toxicities we will consider grade 3 toxicity or premature trial discontinuation as the critical events. The prevalence of events in the letrozole vs. the placebo arm will be examined by Fisher's exact test.

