Evaluation of drug-induced hormonal changes - We will examine whether Letrozole has any effects on serum levels of bioavailable estradiol, and testosterone, determined at baseline and after six months of study medication. We will determine whether addition of letrozole alters the frequency of menopausal symptoms.

Adverse Events and Quality of Life – Change from baseline to six months for hot flash score (Mayo Clinic), fatigue (brief fatigue inventory), overall quality of life (BCPCT), bone turnover markers, HDL/total cholesterol, and C-reactive protein will be compared between the two groups using the two-sample t-test. Similarly, demographic variables (e.g., age, education) and hormonal levels will be tested for use as covariates on each of these endpoints. We will also assess the effects of change in serum hormones (if any) and baseline 25-OH vitamin D levels on incidence and severity of arthralgias and fatigue.

Within Letrozole Comparisons at baseline, 6 and 12 months - On all of our quantitative continuous measures we will perform a repeated measures analysis comparing the 6 and 12 month values to baseline and also with each other. This will give us some preliminary indication whether there is any benefit or detriment of 12 months of treatment. For all the above analyses of exploratory endpoints, as well as for changes in proliferation, results from the 12-month timepoint (following six months of open-label treatment with active agent) will also be analyzed and compared to the baseline and six month values with caution since the double-blind, randomized nature of the comparison is no longer present. However, since

every effort is made to conduct the assessment and quantification of biomarkers without knowledge of treatment arm, the results could be informative.

Since this is a phase IIB trial, the power and sample size for the primary endpoint was determined with a two-sided type I error rate of 5%. All subsequent secondary, tertiary and exploratory analyses will also be tested with a two-sided type I error rate of 5%. This may result in an elevated false positive rate for these secondary and tertiary analyses, however, since this is a Phase IIB study, we felt to control the type I error rate for the secondary, tertiary and exploratory analyses would be too conservative.

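### Section 12.2 pre-specifies no log or ratio-scale analysis for CRP, hormones, the cholesterol ratio or pS2/GREB-1, leaves the pS2/GREB-1 change scale undefined, and inverts the lipid ratio of Objective 1.2

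*Combined protocol and SAP*

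**What the plan says.** For Ki-67, section 12.2 specifies a two-sample t-test on change from baseline to 6 months. ANCOVA is added if baselines differ significantly, and a Wilcoxon signed-rank test is reserved for extreme skewness. For the secondary endpoints, "similar methods as above will be used to compare the treatment and control groups at two time points for all markers". The list that follows names serum hormones, mammographic density and clinical laboratory tests. pS2 and GREB-1 are named only in the next sentence, on correlation with Ki-67 change.

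The adverse event and quality of life paragraph of 12.2 adds that change in "bone turnover markers, HDL/total cholesterol, and C-reactive protein will be compared between the two groups using the two-sample t-test". That sentence gives no transformation and no fallback.

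On the gene measurements, section 10.4 states: "The quantity of RNA is expressed relative to the level of that for a housekeeping gene". In section 2.8 the pilot figure "plots the relative expression for pS2 (6 month value/baseline") against change in Ki-67, so the pilot worked with fold change.

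On lipids, Objective 1.2 names the total cholesterol:HDL ratio, and section 10.5.3 says that CRP and "total cholesterol:HDL ratios provide excellent risk biomarkers for cardiovascular disease". Section 12.2 tests the reciprocal.

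**The concern.** Relative expression by qRT-PCR is read from threshold cycles and is multiplicative by nature. CRP and serum hormones are commonly right-skewed. On such measures an arithmetic difference is dominated by the few women with high baseline values, so a t-test on it can be much less sensitive than one on log change.

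Objective 1.4 carries the argument, made in section 10.4, that letrozole lowers breast tissue estrogen although HRT continues. It may also have fewer usable pairs than Ki-67: in the pilot, 8 of the 14 women with good RNA had valid pS2 at both visits, out of 21 with paired material. With no scale fixed for a stated objective, the choice between arithmetic change and fold change falls after the data are seen.

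For the lipid ratio, harm is a rise in one orientation and a fall in the other. Arithmetic change is not invariant to inversion, so the two are different tests.

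**Working it through.** **1. The plan's own figure.** Section 12.1: "A 1:1 randomization of 96 evaluable subjects will provide 90% power to detect an effect size of 0.67 standard deviations". The test is a t-test between arms at a two-sided level of 0.05. The inputs behind it are an SD of 5.5 and a difference of 3.7 (both in percentage points of Ki-67), so d = 3.7/5.5 = 0.67. Exact t-test power with 48 per arm is 90.1% for d = 0.67 and 90.4% for 3.7/5.5. The stated figure reproduces. No power is stated for any secondary marker.

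**2. Assumptions for a pS2-type marker.** The documents give no SD or within-woman correlation. Assume log-normal values, correlation ρ = 0.5, placebo unchanged, letrozole halving expression, and a log2 SD σ of 0.5, 1.0 or 1.5 at each visit.

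**3. Standardised effects.**
- Log ratio: the effect is log2(0.5) = −1. The SD of change is σ√(2(1−ρ)) = σ, so |d| = 1/σ.
- Arithmetic change: put s = σ·ln 2 and scale by the placebo mean. The difference in mean change is 0.5. The placebo variance is 2(e^{s²} − e^{ρs²}); the letrozole variance is 1.25(e^{s²} − 1) − (e^{ρs²} − 1). Then d = 0.5/√(average variance).
  - σ = 0.5: variances 0.131 and 0.098, d = 1.48.
  - σ = 1.0: variances 0.691 and 0.499, d = 0.65.
  - σ = 1.5: variances 2.462 and 1.718, d = 0.35.

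**4. Simulated power, 48 per arm, two-sided 5%.**

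| log2 SD | d arithmetic | d log | t-test, arithmetic change | rank-sum, arithmetic change | t-test, log ratio |
|---|---|---|---|---|---|
| 0.5 | 1.48 | 2.00 | about 100% | about 100% | about 100% |
| 1.0 | 0.65 | 1.00 | about 90% | 96% | 99.8–99.9% |
| 1.5 | 0.35 | 0.67 | about 48% | 72% | 90% |

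At σ = 1.5 the log-scale effect equals the plan's design effect of 0.67 SD, so 90% is what step 1 predicts.

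**5. Fewer usable pairs.** 8/14 × 48 ≈ 27 per arm. Arithmetic change against log ratio is then about 70% against 95% at σ = 1.0, and about 30% against 67% at σ = 1.5.

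**6. Lipid ratio.** If R is total cholesterol:HDL, the change in 1/R is −(R₂ − R₁)/(R₁R₂), so each woman's change is reweighted. On the log scale log(1/R) = −log R: the t statistic only changes sign and the p-value is identical. With an assumed natural-log SD of 0.20 to 0.35, correlation 0.7 to 0.8 and a true rise of 0 to 15%, power differs between orientations by about 6 points at most (82% for total:HDL against 76% for HDL/total at SD 0.30, correlation 0.7, 15% rise). The two forms disagree on significance in about 0 to 21% of simulated trials, and in 3.5 to 5.6% when there is no effect.

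**The case against.** **The plan has a skewness safeguard.** This is true, and applying the Ki-67 methods to the secondary markers carries it over. It helps only in part. The test named, signed-rank, is paired and cannot compare two arms. The trigger is extreme skewness, with no threshold. The sentence on CRP and lipids does not mention it. If a rank-sum test was meant, on arithmetic change it recovers part of the loss (72% against 90% at log2 SD 1.5). On fold change it would recover nearly all of it (89% against 90%), but the plan does not specify that scale either.

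**The plan does not say that pS2 and GREB-1 are compared as arithmetic change.** This stands. A reader might infer it from the reference to all markers, but the list that follows does not name these genes, and the only scale shown for them is the pilot's fold change. What the documents support is that the scale is undefined.

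**A large power loss cannot be derived from the documents.** This also stands. A reader might infer that much of the power for Objective 1.4 is wasted. That holds at the wider assumed spreads and vanishes at log2 SD 0.5. For CRP and hormones no spread is given, so any tilt towards the predicted absence of a difference cannot be sized.

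**The lipid inversion is a labelling slip.** Largely so. It would be too strong to say that the lipid result hinges on orientation: the power effect is modest, and a two-sided test does not depend on which direction is harm. The inconsistency itself needs no assumption.

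Finally, these are secondary endpoints of a phase IIB trial with no power claim attached.

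**Conclusion.** The concern holds in a limited form. Three facts need no assumption: no log or ratio-scale analysis is pre-specified, although CRP and the cholesterol ratio are explicitly given a t-test on change and hormones default to it; the change scale for pS2 and GREB-1 is undefined; and the lipid ratio in 12.2 is the reciprocal of the one in Objective 1.2 and 10.5.3.

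The size is conditional. For a halving of expression with 48 per arm and correlation 0.5, the loss from arithmetic change runs from nothing at log2 SD 0.5, through about 10 points at 1.0, to about 42 points (90% − 48%) at 1.5. A rank-sum test on arithmetic change would cut the last figure to about 18 points (90% − 72%). For the lipid ratio the loss is about 6 points at most, with some discordance in significance. The primary analysis and the sample size of 96 evaluable women stand.

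**What to change.** In 12.2, state that pS2 and GREB-1 are compared between arms as log2 fold change from baseline (delta-delta-CT, with the sign convention given), and that CRP, bioavailable estradiol, bioavailable testosterone and the cholesterol ratio are compared as log change. Report between-arm geometric mean ratios with 95% confidence intervals. Write the lipid ratio as total cholesterol:HDL throughout; on the log scale the orientation no longer affects the test. If a rank fallback is kept, name a two-sample rank-sum test in place of the signed-rank test.

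The cost is a sentence or two in the plan and no new data. Results are then read as ratios rather than absolute differences, and a rule is needed for values below an assay's detection limit.

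### Correlations of Ki-67 change with pS2 and GREB-1 change carry no arm term in Section 12.2, so the treatment effect alone can produce a significant result

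*Combined protocol and SAP*

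**What the plan says.** Section 12.2, in the paragraph on secondary endpoints, states "We will also correlate change in the primary biomarker Ki-67 with change in other markers". It gives bioavailable estradiol, pS2 and GREB-1 as examples. The statistic is Pearson's coefficient, or Spearman's under high skewness. The text does not say whether the arms are pooled, split or adjusted for.

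The next paragraph of 12.2 plans a multiple regression for change in Ki-67, which also looks at how other biomarkers predict that change. There arm is named: "Best subsets and stepwise approaches will be employed while controlling for treatment group".

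Four other places bear on the point:

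- Section 3.0 expects significant reductions under letrozole in Ki-67 and in expression of the estrogen response genes.
- Section 10.5.2 expects no significant difference between arms in change in estradiol or testosterone.
- Section 10.4 gives the gene assays a mechanistic purpose, to "provide indirect evidence of reduction in breast tissue estradiol through assessment of the estrogen response genes".
- The end of 12.2 tests every secondary and exploratory analysis at a two-sided 5% level.

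**The concern.** If the drug lowers both markers, arm is a common cause of the two changes. In the pooled sample, letrozole women then tend to have low values on both and placebo women high values on both. That separation alone yields a positive correlation, with no tendency for a woman whose pS2 fell further to have a larger fall in Ki-67 than others in her arm.

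The correlation is likely to be read as mechanism. Section 2.8 took the pilot's relation between pS2 change and Ki-67 change as support for lower estrogen at tissue level. The pilot had a single arm (Section 2.6), so that relation was within-arm by construction. The same plain correlation in a two-arm trial answers a different question. Part of it only repeats that each marker differs by arm, which the between-arm comparisons already address.

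**Working it through.** **Inputs from the documents (Section 12.1).** "A 1:1 randomization of 96 evaluable subjects will provide 90% power to detect an effect size of 0.67 standard deviations". The comparison is a t-test of two groups, two-sided at the 5% level. The raw form is "90% power to detect an average change of 3.7% in Ki-67 in the letrozole group", with a "common standard deviation of change of 5.5" percentage points in both arms and zero mean change on placebo.

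**The plan's own figure.** 3.7/5.5 = 0.673 SD. With 48 per arm and 94 degrees of freedom, the noncentral t gives power of 0.904 for 0.673 SD and 0.901 for 0.67 SD. The stated 90% is reproduced. At 10% drop-out, 96/0.90 = 106.7, close to the 108 planned.

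**Inputs that are assumptions.** The documents give no standardised treatment effect for pS2 or GREB-1, so I use 0.3 to 1.0 SD. They give no expected number of RNA pairs either. In the pilot (Section 2.8), 14 of 21 women with paired material had good RNA, and pS2 was valid at both times in 8 of those 14. Carried over, 96 × 14/21 = 64 pairs and 96 × 8/21 = 36.6, taken as 36 pairs (32 and 18 per arm).

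**Induced correlation.** Take 1:1 arms, unit within-arm SD, treatment effects d1 and d2, and zero within-arm correlation. The between-arm part adds d1·d2/4 to the covariance and d²/4 to each variance, so

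r = (d1·d2/4) / √[(1 + d1²/4)(1 + d2²/4)].

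With d1 = 0.67:

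- d2 = 0.3: 0.0503/1.066 = 0.047
- d2 = 0.67: 0.1122/1.112 = 0.101
- d2 = 1.0: 0.1675/1.179 = 0.142

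**Rejection rate of the two-sided 5% test.** Simulated with normal data, zero within-arm correlation, a Ki-67 effect of 0.67 SD and 100,000 trials per cell. Entries are for pooled Pearson.

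| Gene effect (assumed) | Induced r | 96 pairs | 64 pairs | 36 pairs |
|---|---|---|---|---|
| 0 SD | 0.00 | 5.0% | 4.9% | 5.0% |
| 0.3 SD | 0.05 | 7.4% | 6.4% | 5.7% |
| 0.5 SD | 0.08 | 11.7% | 9.3% | 7.3% |
| 0.67 SD | 0.10 | 16.4% | 12.6% | 9.1% |
| 1.0 SD | 0.14 | 28.7% | 20.3% | 13.3% |

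Pooled Spearman agrees to within half a point in every cell, so the planned fallback does not help.

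**Analytic check of one cell.** For r = 0.101 and 96 pairs, Fisher's z gives atanh(0.101) × √93 = 0.98. The chance of exceeding ±1.96 is about 16%, in line with the table.

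**After adjustment.** The correlation of residuals from arm means, tested on N − 3 degrees of freedom, rejects 4.9% to 5.2% of the time in every cell.

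**Conditions.** The 0 SD row is the case that Section 10.5.2 expects for estradiol. If Ki-67 itself has no treatment effect, the pooled test also stays near 5%, whatever the other marker does. Inflation needs an effect on both markers.

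**The case against.** The strongest reply is that 12.2 already has the right analysis: its regression examines other biomarkers as predictors of Ki-67 change with treatment group controlled. That stands as partial mitigation. But the regression selects variables by best subsets and stepwise methods, and the text does not say that the biomarkers enter as changes. The correlations and their p-values would still be reported unadjusted.

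A second reply is that a pooled correlation validly describes the mixed sample, and that if letrozole acts through tissue estrogen, covariation caused by the drug belongs to the pathway. The description is valid. It still cannot separate that pathway from two unrelated drug effects, so it adds little to the arm comparisons.

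A third is that 12.2 openly accepts more false positives in secondary analyses. That passage concerns many uncorrected tests. It does not address one test whose own error rate departs from 5% because of arm.

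A reader might also infer more than the documents support:

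- *That all three named markers are affected.* Sections 3.0 and 10.5.2 expect no arm difference in serum hormones, so the estradiol test is not expected to be inflated.
- *That the error rate reaches about half.* It takes 1.0 SD effects on both markers to reach about 51% with 96 pairs. For Ki-67 that means a 5.5-point mean fall from a pilot baseline of 6.4% (5.5/6.4 = 86%), against the planned 3.7 points (58%).
- *That 96 gene pairs will be available.* Pilot RNA yield suggests fewer. Sections 4.3 and 10.1 require extra cells and a slide for RNA, so yield may improve, but 96 is the planned ceiling.
- *That the plan states a pooled test.* It does not. The unadjusted reading rests on the missing arm term, set against the explicit one in the next paragraph.

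**Conclusion.** The point holds for pS2 and GREB-1 and is minor. Run as written on pooled data, their correlation tests with Ki-67 would not keep a 5% error rate as tests of association within arm. Taking Section 12.1's Ki-67 effect of 0.67 SD and assumed gene effects of 0.3 to 1.0 SD, the rate is about 7% to 29% with 96 pairs, and about 6% to 20% with 36 to 64 pairs. The induced correlations are small, about 0.05 to 0.14. The figures rest on normal data, equal arms and zero within-arm correlation. The gene effects and RNA yields are assumptions. The primary t-test, the sample size and the safety comparisons are untouched.

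**What to change.** In Section 12.2, replace the plain correlation with a partial correlation between change in Ki-67 and change in each other marker, adjusted for randomised arm and computed on ranks if the data are skewed. Report the arm-specific correlations beside it with confidence intervals and the number of pairs, since the partial correlation summarises one common association across arms. Apply the same rule to every marker, estradiol included. For estradiol, adjustment costs one degree of freedom and guards against an unexpected arm difference.

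The change is one phrase plus a display by arm. It uses the same data and software and needs no additional participants, so it is a free improvement.
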